Version:	5	User Tool ID:	16.2.6UserTool0004		
Status:	Final	User Tool Version Date	5June2019	Page:	10

1. STATEMENT OF COMPLIANCE

This study will be carried out in accordance with International Conference on Harmonization Good Clinical Practice (ICH GCP) and the following:

United States (US) Code of Federal Regulations (CFR) applicable to clinical studies (45 CFR Part 46, 21 CFR Part 50, 21 CFR Part 56, 21 CFR Part 312, and/or 21 CFR Part 812).

The protocol, informed consent form, recruitment materials, and all participant materials will be submitted to the Institutional Review Board (IRB) for review and approval. Approval of both the protocol and the consent form must be obtained before any participant is enrolled. Any amendment to the protocol will require review and approval by the IRB before the changes are implemented in the study. In addition, all changes to the consent form will be IRB-approved; a determination will be made regarding whether a new consent needs to be obtained from participants who provided consent using a previously approved consent form.

Document ID:	SRC_SLE_Sparkle_P SG_2020_10908	Document title:		Classification:	Confidential
Modified:	26 July 2021	Clinical Investigation Protocol ICH E6 Aligned			
Version:	5	User Tool ID:	16.2.6UserTool0004		
Status:	Final	User Tool Version Date	5June2019	Page:	11

2. PROTOCOL SUMMARY

2.1. Synopsis

Study Title & ID:	Diagnostic validation of the DreamKit device against polysomnography SRC_SLE_Sparkle_PSG_2020_10908
Project Name:	Sparkle
Study Design:	Multi-center validation study.
Objective:	The objective of this study is to demonstrate the diagnostic efficacy of the DreamKit device against the gold-standard comparator, polysomnography (PSG), amongst a sample of $n=200$ participants with and without sleep-disordered breathing (SDB).
Endpoints:	
Primary Endpoint: The intraclass correlation coefficient (ICC) for absolute agreement between the PSG- apnea hypopnea index (AHI) and DreamKit-AHI.
 
Secondary Endpoint: The ICC for absolute agreement between the PSG- central apnea index (CAI) and DreamKit-CAI.

Hypotheses:	
Hypothesis 1 (Primary): We hypothesize that the lower-bound of the ICC 95% confidence interval (CI) between the PSG-AHI and DreamKit-AHI will be ≥ 0.75, indicating good reliability.
 
Hypothesis 2 (Secondary): We hypothesize that the lower-bound of the ICC 95% CI between the PSG-CAI and DreamKit-CAI will be ≥ 0.50, indicating moderate reliability.

Study Sample:	
Up to $n=280$ participants will be enrolled, in order for $n=200$ participants to complete the study with valid data.
 
Inclusion Criteria:
 
 • INCL1: Aged ≥ 18 years; • INCL2: Fluent in English; • INCL 3: Able to provide informed consent.

Document ID:	SRC_SLE_Sparkle_PSG_2020_10908	Document title:	Classification:	Confidential
Modified:	26 July 2021	Clinical Investigation Protocol ICH E6 Aligned		
Version:	5	User Tool ID:	Page:	12
Status:	Final	User Tool Version Date		

	
Exclusion Criteria:
 
 • EXCL 1: Self-reported habitual sleep duration of <4 hours/night on average ("How many hours sleep do you usually get per night?"); • EXCL 2: Circadian phase disorder, shift work, or any other issue/condition that would, in the opinion of the site investigator, reduce the likelihood of obtaining at least four hours of sleep during the overnight study; • EXCL 3: History of allergic reactions to medical adhesives; • EXCL 4: Skin rash or other dermatological condition that would impact correct placement of the DreamKit device and/or PSG sensors, and/or would be exacerbated by the presence of the device or sensors; • EXCL 5: Presence of a pacemaker; • EXCL 6: Severe medical condition (controlled or uncontrolled) that would impede data collection in the opinion of the site investigator, including the requirement for oxygen therapy; • EXCL 7 [for those currently using overnight therapy]: Unwilling to withdraw from overnight therapy for a single night and/or clinically unsuitable to withdraw from overnight therapy in the opinion of the site investigator, with overnight therapy including but not limited to any form of positive airway pressure (PAP) or ventilation, oral device including mandibular advancement devices or mouthguard for bruxism, nasal dilator strips, and/or positional device; • EXCL 8 [for those currently using overnight therapy]: Considered by the site investigator to be at risk of an adverse event (AE) resulting from hypersomnolence the day after the overnight visit, such as a high-risk occupation including but not limited to a pilot or commercial driver; • EXCL 9: An employee, or family member of an employee, of a company that designs, sells, or manufactures sleep related products (including Philips).
--	--

Document ID:	SRC_SLE_Sparkle_P SG_2020_10908	Document title:		Classification:	Confidential
Modified:	26 July 2021	Clinical Investigation Protocol ICH E6 Aligned			
Version:	5	User Tool ID:	16.2.6UserTool0004		
Status:	Final	User Tool Version Date	5June2019	Page:	13

Clinical Investigation Protocol ICH E6 Aligned

Study Visits Summary & Duration:	Visit 1: Consent, anthropometrics, vital signs, questionnaires. Visit 2: Overnight, attended PSG with simultaneous DreamKit recording.
----------------------------------	---

Document ID:	SRC_SLE_Sparkle_P SG_2020_10908	Document title:		Classification:	Confidential
Modified:	26 July 2021	Clinical Investigation Protocol ICH E6 Aligned			
Version:	5	User Tool ID:	16.2.6UserTool0004		
Status:	Final	User Tool Version Date	5June2019	Page:	14

2.2. Schedule of Activities

Procedures	Performed by	Visit 1 (office visit)	Visit 2 (overnight)
Informed Consent	Principal Investigator or designee	X	
Anthropometrics and vital signs	Study coordinator	X	
Questionnaire battery	Study coordinator	X	
Sleep study	Technologist		X
Data download and transfer	Study coordinator		X
Adverse event (AE) Monitoring	Study coordinator	X	X
Participant compensation & Study Dismissal	Study coordinator		X

Document ID:	SRC_SLE_Sparkle_P SG_2020_10908	Document title:		Classification:	Confidential
Modified:	26 July 2021	Clinical Investigation Protocol ICH E6 Aligned			
Version:	5	User Tool ID:	16.2.6UserTool0004		
Status:	Final	User Tool Version Date	5June2019	Page:	15

3. INTRODUCTION

3.1. Study Rationale

The primary objective of this study is to assess the diagnostic performance of the DreamKit device against the gold-standard comparator, polysomnography (PSG), amongst a sample of $n=200$ participants with and without sleep-disordered breathing (SDB). Data will be used as evidence to support the proposed intended use statement, described in Section 4.4 below.

Please see ER2235417 (Clinical Strategy & Clinical Development Plan Document – Sparkle) for a comprehensive overview of the clinical development plan for this product. This protocol has been designed to address Evidence ID 006 of ER2235417 (Version 2).

3.2. Background

Home sleep apnea test (HSAT) devices are increasingly used to diagnose obstructive sleep apnea (OSA).¹ Potential advantages of taking the diagnostic process from the hospital to the home include reduced cost; increased access; reduced wait times; higher patient turnover; increased patient comfort; and the collection of data that is more representative of a patient's usual sleep. Drawbacks of the HSAT model include the reduced number of signals compared with PSG; reduced patient/provider contact thereby limiting the opportunity for OSA education/support; and increased possibility of configuration error or signal loss leading to the requirement for further testing.¹⁻³ Research has demonstrated that a lab-based diagnostic approach is not superior to a home-based approach in terms of self-reported daytime sleepiness, quality of life, blood pressure, and subsequent adherence to positive airway pressure (PAP) measured over four weeks.⁴ Development of a simpler HSAT device may be beneficial in terms of maximizing the collection of good quality signals, while also increasing ease of use and patient comfort. The DreamKit device has been designed to meet these needs.

The DreamKit is a single-use adhesive patch containing an accelerometer and pulse oximeter, linked to nasal pressure cannulae. From these three sensors, the following signals can be monitored or derived: nasal airflow, blood oxygen saturation (SpO_2), pulse rate, respiratory effort, sleep time, and head position. The adhesive patch containing the pulse oximeter is designed to be placed on the forehead, connected to adhesive nasal pressure cannulae placed over the nasal bridge and directly below the nostrils. Data are stored in the flash memory on the device, and can be uploaded to a computer upon completion of the recording.

Document ID:	SRC_SLE_Sparkle_PSG_2020_10908	Document title:		Classification:	Confidential
Modified:	26 July 2021	Clinical Investigation Protocol ICH E6 Aligned			
Version:	5	User Tool ID:	16.2.6UserTool0004		
Status:	Final	User Tool Version Date	5June2019	Page:	16

4. OBJECTIVES

The objective of this study is to demonstrate the diagnostic efficacy of the DreamKit device against the gold-standard comparator, PSG, amongst a sample of $n=200$ participants with and without SDB.

4.1. Endpoints

Primary Endpoint: The intraclass correlation coefficient (ICC) for absolute agreement between the PSG-apnea-hypopnea index (AHI) and DreamKit-AHI.

Secondary Endpoint: The ICC for absolute agreement between the PSG-central apnea index (CAI) and DreamKit-CAI.

4.2. Hypotheses

Hypothesis 1 (Primary): We hypothesize that the lower-bound of the ICC 95% confidence interval (CI) between the PSG-AHI and DreamKit-AHI will be ≥ 0.75 , indicating good reliability.⁵

Hypothesis 2 (Secondary): We hypothesize that the lower-bound of the ICC 95% CI between the PSG-CAI and DreamKit-CAI will be ≥ 0.50 , indicating moderate reliability.⁵

4.3. Exploratory Analyses

Exploratory analyses will include investigating reliability of the 3% oxygen desaturation index (ODI3%), total respiratory events, total apneas, total hypopneas, total obstructive apneas, total central apneas, and total mixed apneas; agreement of the AHI categorized according to American Academy of Sleep Medicine AASM thresholds for mild/moderate/severe SDB; diagnostic performance metrics at clinically-relevant thresholds of the AHI, CAI, and ODI3%; event-level differentiation of events; and a comparison of signal quality between the DreamKit and PSG. The primary and secondary analyses will adopt the AASM recommended criteria for identifying hypopneas; in exploratory analyses we will also investigate the impact of using the alternative criteria.

4.4. Claims and Intended Performance

The proposed intended use statement for DreamKit is as follows, with the parts relevant to this study bolded (wording may change before regulatory submission):

*The DreamKit device is a physiologic data recorder intended to collect and record data for use by clinical software used in polysomnography and sleep disorder studies **for the diagnosis of sleep related breathing disorders**. The Plethysmography-Acquired Respiratory Effort (PARE) algorithm provides a respiratory effort signal acquired from the DreamKit photoplethysmography signal that correlates with traditional respiratory effort signals used in polysomnography. The DreamKit with PARE provides the information required to **detect apneas and hypopneas and classify these***

Document ID:	SRC_SLE_Sparkle_PSG_2020_10908	Document title:		Classification:	Confidential
Modified:	26 July 2021	Clinical Investigation Protocol ICH E6 Aligned			
Version:	5	User Tool ID:	16.2.6UserTool0004		
Status:	Final	User Tool Version Date	5June2019	Page:	17

respiratory events as central, mixed, or obstructive. It is intended for adult use and can be used in a hospital, clinic, or patient home.

4.5. Considerations regarding study endpoints

4.5.1. Rationale for the selection of endpoints

The table below summarizes the respiratory parameters required to be reported for HSATs in clinical settings, per the AASM Scoring Manual (Version 2.6). We prioritized the AHI and CAI for our primary and secondary hypotheses, respectively, and included all other listed variables in our exploratory analyses.

Table 1: AASM reporting requirements for adult HSAT reports

Parameter	AASM Reporting Requirement	Endpoint
Respiratory event index* (REI); events/hour	Recommended	Primary (continuous) Exploratory (4-category and binary)
CAI; events/hour	Optional	Secondary (continuous) Exploratory (binary)
Number of respiratory events	Recommended	Exploratory (continuous)
Number of apneas	Recommended	Exploratory (continuous)
Number of hypopneas	Recommended	Exploratory (continuous)
Number of obstructive apneas	Optional	Exploratory (continuous)
Number of central apneas	Optional	Exploratory (continuous)
Number of mixed apneas	Optional	Exploratory (continuous)
A measure of SpO ₂ saturation:	Recommended	Exploratory (continuous) [based on ODI3%]
• ODI3% or ODI4%		
• SpO ₂ Mean/maximum/minimum		
• Percentage of time <88% or other SpO ₂ threshold		

The AASM scoring manual (Version 2.6) Section IX, Part 1, stipulates that recommended parameters must be reported, and that optional parameters may be monitored at the discretion of the clinician or investigator and if monitored, should be reported.

* Throughout this document, we refer to the AHI rather than the REI, as the DreamKit includes a measurement of sleep (see Section 8.1.5).

4.5.2. Rationale for the identification of performance thresholds

We adopted the standards of Koo and Li (2016)⁵ and identified a performance target of ≥ 0.75 for the lower-bound of the 95% CI of the ICC for the AHI, representing good reliability. A meta-analysis of 13 studies representing $n=853$ participants reported agreement between the PSG-AHI and the WatchPAT-AHI, falling into the same category of good reliability (0.893; 95% CI 0.857 – 0.920) (the exact type of correlation coefficient in this paper was not specified).⁶

Document ID:	SRC_SLE_Sparkle_PSG_2020_10908	Document title:		Classification:	Confidential
Modified:	26 July 2021	Clinical Investigation Protocol ICH E6 Aligned			
Version:	5	User Tool ID:	16.2.6UserTool0004		
Status:	Final	User Tool Version Date	5June2019	Page:	18

Clinical Investigation Protocol ICH E6 Aligned

We identified a performance target of ≥ 0.50 for the lower-bound of the 95% CI of the ICC for the CAI, representing moderate reliability. In their recent 510(k) submission for the Nox Sleep System (K192469; November 13th, 2019), Nox Medical adopted the same analysis along with a target of 0.46, as has been reported elsewhere in the literature.⁷

Neither the WatchPAT nor Nox Sleep System are the predicate device for DreamKit; however, they are comparable devices with similar intended use statements to the DreamKit, all of which claim to be a diagnostic aid for sleep disorders. The Watch-PAT300 (Itamar Medical; Caesarea, Israel) is an FDA-approved (K153070) HSAT device which uses finger peripheral arterial tonometry, heart rate, and oxygen saturation to identify respiratory events and estimate sleep staging in the compatible zzzPAT software. The Nox Sleep System (Nox Medical; Reykjavik, Iceland) is an FDA-approved (K192469) platform consisting of a HSAT device, PSG device, software, mobile platform, and accessories.

4.6. Inclusion of Actigraphy

For exploratory product development purposes, we will also collect data from a wrist actigraphy device (GENEActiv Original; Activinsights). The actigraphy data will not contribute to any DreamKit analyses. The presence of the actigraphy device is akin to a participant sleeping with a regular wristwatch, and will therefore not impact the data used for the DreamKit analyses.

The safety or efficacy of the actigraphy device is not under investigation. The use of these devices is to collect data for exploratory purposes.

Document ID:	SRC_SLE_Sparkle_PSG_2020_10908	Document title:		Classification:	Confidential
Modified:	26 July 2021	Clinical Investigation Protocol ICH E6 Aligned			
Version:	5	User Tool ID:	16.2.6UserTool0004		
Status:	Final	User Tool Version Date	5June2019	Page:	19

5. STUDY DESIGN

5.1. Overall Design

This is a multi-center study performed for the purpose of diagnostic validation. Up to $n=280$ participants will be enrolled, in order for $n=200$ participants to complete the study with evaluable data. Completion of the protocol by an individual participant will require an office visit of approximately one hour followed by an overnight laboratory visit of approximately 12 hours, to take place within a six week period. If convenient, the two visits may be combined. Total enrollment duration for an individual participant will not exceed six weeks; it is estimated that the entire study duration will not exceed nine months.

5.2. Scientific Rationale for Study Design

The study has been designed to align with the Standards for Reporting Diagnostic Accuracy (STARD) statement.⁸

5.3. Justification of Treatment Regimen and Duration

No treatment will be implemented during this study.

5.4. Measures to Minimize Bias

This study is designed for the purpose of diagnostic validation, and therefore randomization and blinding will not take place.

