6.5. Strategies for Recruitment and Retention

Participants will be recruited such that the overall sample will comprise approximately 50% OSA, 30% central sleep apnea (CSA; with or without Cheyne-Stokes respiration), and 20% healthy (no SDB). Recruitment for the OSA and CSA participants will proceed by targeting those with a known diagnosis and/or those currently using therapy for SDB and/or those considered by the site investigator to be high-risk. The sites may choose to administer the STOP-BANG questionnaire⁹ during phone screening for risk stratification, but this is optional. Due to night-to-night SDB severity variability as well as the natural history of SDB, the diagnosis of each participant may not be known ahead of time and as such, our inclusion/exclusion criteria do not reference OSA or CSA diagnostic criteria.

The PSGs will be scored throughout the study, and each participant will be assigned to a diagnostic category (see Section 8.1.6). This information will be used to guide further recruitment to ensure the proportions of OSA, CSA, and no SDB referenced above, as well as to ensure a wide range of SDB severity. The diagnostic category assigned in this study will be based solely on PSG scoring output without any other clinical information, and will have no bearing on clinical care.

It is anticipated that racial/ethnic minorities will represent at least 20% of the sample, and that males and females will comprise at least 30% of the sample each. These parameters are approximate expectations only.

Document ID:	SRC_SLE_Sparkle_PSG_2020_10908	Document title:		Classification:	Confidential
Modified:	26 July 2021	Clinical Investigation Protocol ICH E6 Aligned			
Version:	5	User Tool ID:	16.2.6UserTool0004		
Status:	Final	User Tool Version Date	5June2019	Page:	22

Clinical Investigation Protocol ICH E6 Aligned

All participants will be enrolled within the US. Recruitment will be the responsibility of the site, and will take place through advertisements, the pipeline at local clinic/s, and/or by inspection of local medical records. As this study has only two visits, it is not likely that participants will drop-out or be lost to follow-up before study completion and therefore no specific strategies for retention are required.

Document ID:	SRC_SLE_Sparkle_P SG_2020_10908	Document title:		Classification:	Confidential
Modified:	26 July 2021	Clinical Investigation Protocol ICH E6 Aligned			
Version:	5	User Tool ID:	16.2.6UserTool0004		

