8.1.5. Data processing and scoring

All data processing will take place at Philips using Sleepware software. The analyst will import the DreamKit and PSG signals, ensuring that the signals are mapped correctly. The analyst will then inspect the time alignment of the DreamKit and PSG signals; if necessary, the DreamKit time may be adjusted to ensure synchronization with the PSG pulse rate and/or flow signal/s recorded from the shared nasal cannula.

Automated scoring using Somnolyzer will be used for PSG and DreamKit respiratory event detection within the rest period (time between lights off and lights on). Sleep staging during the rest period will be undertaken using Somnolyzer (PSG) or CReSS (DreamKit) algorithms. Sleep staging and event scoring will follow AASM guidelines.¹⁴ Apneas will be scored when there is a ≥90% reduction in airflow for at least ten seconds (Section IX Part 1, G1), and classified as obstructive (continued or increased respiratory effort throughout), central (absence of respiratory effort throughout), or mixed (initial absence followed by resumption of respiratory effort). For our primary and secondary analyses, hypopneas will be scored according to the AASM recommended criteria; that is, a ≥30% reduction in airflow for at least ten seconds, associated with a SpO₂ desaturation of ≥3% (Section IX Part 1, H1A). We will perform a sensitivity analysis in which hypopneas are scored according to the alternative criteria (a ≥30% reduction in airflow for at least ten seconds, associated with a SpO₂ desaturation of ≥4%; Section IX Part 1, H1B).

The following metrics will be calculated for both the PSG and DreamKit:

- AHI: Number of apneas and hypopneas divided by TST;
- CAI: Number of central apneas divided by TST;
- ODI: Number of SpO₂ desaturations (≥3%) divided by TST.

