8.1.6. Signal quality and other feedback to sites

Data processing and scoring will take place throughout the study, allowing continual feedback from Philips to the sites.

The AASM clinical practice guidelines state that a diagnosis can be made using a HSAT only if the recording includes at least four hours of technically adequate oximetry and flow data;¹⁵ studies that do not meet these criteria will not be included in the evaluable dataset. Collection of persistent invalid PSGs or other quality issues may prompt Philips to request the site to undergo troubleshooting or re-training. Note that if a PSG is excluded from the evaluable dataset for technical reasons but the investigator considers the participant to be suitable for a repeat test, a repeat overnight visit can be scheduled.

Each PSG will be categorized as follows (note that these categories are not mutually exclusive; as such, groups will be filled in the order listed below):

- PSG-CAI ≥30 events/hour (~10% of sample);

Document ID:	SRC_SLE_Sparkle_PSG_2020_10908	Document title:		Classification:	Confidential
Modified:	26 July 2021	Clinical Investigation Protocol ICH E6 Aligned			
Version:	5	User Tool ID:	16.2.6UserTool0004		
Status:	Final	User Tool Version Date	5June2019	Page:	28

- PSG-OAI ≥30 events/hour (~17% of sample);
- PSG-CAI 15-29.9 events/hour (~10% of sample);
- PSG-OAI 15-29.9 events/hour (~17% of sample);
- PSG-CAI 5-14.9 events/hour (~10% of sample);
- PSG-OAI 5-14.9 events/hour (~17% of sample);
- PSG-AHI <5 events/hour (~20% of sample).

The proportion of participants falling into these categories across all sites will be conveyed to sites periodically, along with guidance to optimize recruitment according to the approximate goals listed in Section 6.5. Note that the category assigned during this process may differ from a clinical diagnosis; this process will take place only to ensure that recruitment proceeds according to the description in Section 6.5.

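### Section 5.4 rules out blinding, and nothing requires recordings to be judged technically adequate before the DreamKit AHI and CAI can be seen

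*Combined protocol and SAP*

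**What the plan says.** - **Bias protection (5.4).** The section is a single sentence: since the purpose is diagnostic validation, "randomization and blinding will not take place". No other safeguard is listed there.
- **Who processes the data (8.1.5).** "All data processing will take place at Philips using Sleepware software". One analyst role handles both signal sets: "The analyst will import the DreamKit and PSG signals, ensuring that the signals are mapped correctly". The analyst also inspects the alignment, and "if necessary, the DreamKit time may be adjusted to ensure synchronization with the PSG pulse rate" or the shared-cannula flow.
- **Scoring (8.1.5).** "Automated scoring using Somnolyzer will be used for PSG and DreamKit respiratory event detection within the rest period". Sleep staging is automated too.
- **Timing (8.1.6, 6.5).** "Data processing and scoring will take place throughout the study, allowing continual feedback from Philips to the sites". For recruitment steering, 6.5 refers only to the reference test: "The PSGs will be scored throughout the study". The recruitment categories in 8.1.6 are all PSG-derived.
- **Adequacy (8.1.6).** A recording with less than four hours of oximetry and flow of adequate technical quality is left out of the evaluable dataset. The four hours are fixed. What makes a signal adequate is not defined, and no decision-maker is named.
- **Consequence (12.1.2, 9.3, 12.5).** The primary and secondary analyses use the evaluable dataset only. Recruitment goes on until that set is full, and nothing is imputed. No analysis that brings excluded recordings back is planned.

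**The concern.** A paired comparison of two devices on the same night has nothing to randomize. It does have something to blind: whoever decides which pairs count can be kept from seeing how well each pair agrees. Section 5.4 treats both as inapplicable for the same reason, and the reason covers only the first.

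The exposure is narrow. Event detection and staging are automated, so the scores themselves are not at issue. The issue is the undefined adequacy call, made at a time when both indices for that night may already exist. If a large DreamKit-PSG difference prompts a harder look at signal quality, discordant pairs leave the analysis more often than concordant ones and are replaced by new recordings. The ICC then rises for a reason unrelated to device performance. The lower limit of a 95% CI no longer carries its usual false-success rate of 2.5%.

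**Working it through.** **Inputs.** Pass rules: lower 95% limit at or above 0.75 for AHI (12.1.5) and 0.50 for CAI (12.1.6). Analysed size: 200 (5.1, 12.1.1). Pilot AHI ICC: 0.908, lower limit 0.879 (12.1.1). The plan gives no figure for adequacy exclusions or their effect, so there is none to reproduce. The selection patterns below are assumptions.

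**Model.** For recording i and device j, X_ij = s_i + e_ij, both normal, with Var(s) = ρ and Var(e) = 1 − ρ, and no systematic device difference. ρ is set exactly on the threshold, so any pass is a false success.

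**Statistic.** With n = 200, k = 2 and two-way mean squares for recordings (MSR), devices (MSC) and error (MSE):

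ICC = r = (MSR − MSE) / [MSR + (k − 1)MSE + k(MSC − MSE)/n]

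Lower limit = n(MSR − F·MSE) / {F[k·MSC + (kn − k − n)MSE] + n·MSR}

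F is the 97.5% point on n − 1 and v degrees of freedom, where v = (a·MSC + b·MSE)² / {(a·MSC)²/(k − 1) + (b·MSE)²/[(n − 1)(k − 1)]}, a = kr/[n(1 − r)] and b = 1 + kr(n − 1)/[n(1 − r)].

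Dropping pairs with large |X_i1 − X_i2| shrinks MSE and so raises both quantities.

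**Results** (2,000 to 4,000 simulated trials per row, always 200 kept):

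| Exclusion pattern | AHI, true 0.75 | CAI, true 0.50 |
|---|---|---|
| No selection | 2.6% | 2.6% |
| Base exclusion 5%, doubled for the 10% most discordant | 3.1% | 3.4% |
| Base 5%, tripled | 4.6% | 4.9% |
| Base 10%, doubled | 4.6% | 4.4% |
| Base 10%, tripled | 9.4% | 8.4% |
| 10 dropped at random from the most discordant quarter | 11% | 10% |
| 10 dropped at random from the most discordant tenth | 26% | 25% |
| The 4 most discordant dropped | 15% | 14% |
| The 10 most discordant dropped | 46% | 44% |

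Ten exclusions unrelated to the difference leave the AHI rate at 2.5%, so it is the link to the difference that does the damage, not exclusion as such.

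The mechanism shows in the averages. For AHI, the mean ICC moves from 0.748 to 0.776 with the 4 most discordant dropped and to 0.801 with 10; the mean lower limit moves from 0.680 to 0.714 and 0.745.

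**Away from the threshold.** At a true AHI ICC of 0.908, or even 0.879, the chance of passing is about 100% with or without the 4 most discordant pairs.

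**The case against.** The plan has real protections. Scoring and staging are automatic, the four-hour floor is fixed, and flow comes from one cannula split to both systems (8.1.3), so a cannula failure affects both records. Section 5.4 pairs blinding with randomization and may never have been meant to address adequacy decisions. All of this stands. It narrows the exposure to one judgement but does not put that judgement ahead of the indices.

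Four stronger readings are tempting, and the documents do not support them:

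- **Time alignment as a main route of bias.** AHI and CAI are whole-night counts divided by total sleep time (8.1.5). A clock shift cannot re-match events in these indices; it only moves the edges of the rest period. It matters mainly for the exploratory epoch-level tables in 12.1.8.
- **Repeat nights as a main route.** Section 8.1.6 offers a repeat only after a PSG is excluded for technical reasons and the investigator finds the participant suitable. Nothing sends DreamKit indices to sites.
- **Up to 80 adequacy exclusions allowed.** The gap of 280 − 200 = 80 counts from consent (6.3), so it also covers screen failures (6.4), withdrawals (9.1) and loss to follow-up (9.2). No number of adequacy exclusions is stated.
- **An expected false-success rate of 14% or 45%.** Those figures need the most discordant pairs, and only those, to be removed. That is deliberate trimming. Closer scrutiny without intent resembles the upper rows of the table.

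**Conclusion.** The point holds as a gap in the order of decisions. Section 5.4 dismisses blinding for a reason that does not reach exclusion decisions, and 8.1.5 and 8.1.6 leave DreamKit indices potentially visible when adequacy is judged. That the sponsor makes this judgement is inferred from those sections, not stated. A reader might conclude that biased exclusion is planned or likely; the documents show only that nothing prevents it.

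The size is a range that depends on an unknown degree of selection. Against about 2.6% with none, it is about 3.5% to 8% under moderate extra scrutiny (single simulation results from 3.1% to 9.4%), about 10% to 25% under targeted dropping of 10 recordings, and about 14% or 45% in the worst case of 4 or 10. These figures assume normal data, no device bias, 200 kept and a true ICC exactly on the threshold. They bear on pass or fail only if the true ICC lies near the threshold; near the AHI pilot value the effect on passing is negligible.

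The change is still worth making. These data are meant to support the intended-use statement (3.1, 4.4), and protection costs almost nothing.

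**What to change.** - **In 5.4 and 8.1.6,** state that the adequacy of each recording (four hours of oximetry and flow) is decided from the raw signals, and recorded with its reason, before any DreamKit AHI, CAI or ODI for that night is generated or viewed.
- **In 8.1.6,** state that recruitment feedback uses PSG-derived categories only, as 6.5 already implies.
- **In 8.1.5 and 8.1.6,** require a log of every exclusion and every time shift.
- **In 12.1.8,** add a sensitivity analysis of both ICCs that includes every scorable paired recording, whatever its adequacy decision.

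The cost is a change in the order of processing steps, some protocol wording, a log and one further analysis. Sample size, visits and endpoints do not change. The one downside is that DreamKit indices for a night cannot inform feedback until that night's adequacy decision is recorded; feedback on raw-signal quality is unaffected.
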